### 9.3.4. Management of Pericardial toxicity

Subjects will be assessed for evidence of pericardial events during scheduled visits according to the schedule in Table 10-1. The following findings would heighten suspicion of pericardial effusion or pericarditis and prompt immediate evaluation by ECHO:

Symptoms: shortness of breath, orthopnea, chest pain, dizziness, rapid pulse

- Clinical exam: hypotension, jugular venous distension, pulsus paradoxus, faint heart sounds, friction rub, and/or arrhythmia
- ECG: sinus tachycardia, atrial fibrillation, atrial flutter, low voltage with non specific ST-T wave changes and ST elevation or PR depressions, arrhythmia
- Chest X-ray: widening cardiac silhouette

ECHOs will categorize pericardial fluid as minimal (or trivial), small, moderate or large and will assess for hemodynamic compromise.

Pericardial effusions will be assessed as follows (Table 9-4):

• Minimal (or trivial): A small echo-free space in the posterior atrioventricular groove that is visible only in systole when the heart has pulled away from the pericardium. Typically represents a normal amount of pericardial fluid in a disease-free state.

- Small: <1 cm of posterior echo-free space, with or without fluid accumulation elsewhere, present throughout the cardiac cycle, including diastole (and not only systole).
- Moderate: 1 to 2 cm of echo-free space. Moderate effusions tend to be seen along the length of the posterior wall but not anteriorly.
- Large: >2 cm of maximal separation. Large effusions tend to be seen circumferentially.
- Hemodynamic compromise: RV compression, IVC dilation without respiratory variation, abnormal flow variation across the AV valves without respiratory variation, enlarged or collapsed ventricles. RA diastolic collapse in isolation is too non-specific to signal hemodynamic compromise, but should be considered consistent with this diagnosis when accompanied by other findings

Category	Definitions	Subject Management	

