### Echocardiograms

Echocardiogram (ECHO) will be used to assess LVEF at screening and obtain baseline presence of pericardial effusion at start of study.

Echocardiograms will be performed at screening, on Cycle 1 Day 1 (prior to administration of study drug), cycle 1 day 15, cycle 2 day 1, cycle 2 day 15 and repeated as clinically indicated and at End of Treatment. Echocardiograms may be repeated more frequently at the investigator's discretion if signs and symptoms of cardio-toxicity exist. Alternatively, cardiac MRI may be utilized as clinically indicated. If an echocardiogram is performed for screening  $\leq$  7 days before the first dose of study treatment, it does not need to be repeated on Day 1 of Cycle 1.

LVEF assessment and evaluation of pericardial effusions may be performed as clinically indicated at the investigator's discretion if there are signs or symptoms of cardiotoxicity. In case of clinically significant abnormalities, they should be reported in CRDB.

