### 11.0 TOXICITIES/SIDE EFFECTS

#### 11.1. Adverse events

#### 11.1.1. Definitions and reporting

An adverse event is defined as the appearance of (or worsening of any pre-existing) undesirable sign(s), symptom(s), or medical condition(s) that occur after patient's signed informed consent has been obtained. Abnormal laboratory values or test results occurring after informed consent constitute adverse events only if they induce clinical signs or symptoms, are considered clinically significant, require therapy (e.g. hematologic abnormality that requires transfusion or hematological stem cell support), or require changes in study medication(s).

Adverse events that begin or worsen after informed consent should be recorded in CRDB. Conditions that were already present at the time of informed consent should be recorded in the Medical History in CRDB. Adverse event monitoring should be continued for at least 30 days following the last dose of study treatment. Adverse events (including lab abnormalities that constitute AEs) should be described using a diagnosis whenever possible, rather than individual underlying signs and symptoms. When a clear diagnosis cannot be identified, each sign or symptom should be reported as a separate Adverse Event.

Adverse events will be assessed according to the Common Terminology Criteria for Adverse Events (CTCAE) version 4.03. If CTCAE grading does not exist for an adverse event, the severity of mild, moderate, severe, and life-threatening, corresponding to Grades 1 - 4, will be used. CTCAE Grade 5

(death) will not be used in this study; rather, information about deaths will be collected though a Death form.

The occurrence of adverse events should be sought by non-directive questioning of the patient (subject) during the screening process after signing informed consent and at each visit during the study. Adverse events also may be detected when they are volunteered by the patient (subject) during the screening process or between visits, or through physical examination, laboratory test, or other assessments. As far as possible, each adverse event should be evaluated to determine:

1. The severity grade (CTCAE Grade 1-4)

2. Its duration (Start and end dates)

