3. Its relationship to the study treatment (Reasonable possibility that AE is related: No, Yes) or its relationship to the study treatment (Reasonable possibility that AE is related: No, Yes, investigational treatment, Yes, the study treatment (non-investigational), Yes, both and/or indistinguishable)

4. Action taken with respect to study or investigational treatment (none, dose adjusted, temporarily interrupted, permanently discontinued, unknown, not applicable)

5. Whether medication or therapy taken (no concomitant medication/non-drug therapy, concomitant medication/non-drug therapy)

6. Outcome (not recovered/not resolved, recovered/resolved, recovering/resolving, recovered/resolved with sequelae, fatal, unknown)

7. Whether it is serious, where a serious adverse event (SAE) is defined as in Section 11.2.1

All adverse events should be treated appropriately. If a concomitant medication or non-drug therapy is given, this action should be recorded in CRDB.

Once an adverse event is detected, it should be followed until its resolution or until it is judged to be permanent, and assessment should be made at each visit (or more frequently, if necessary) of any changes in severity, the suspected relationship to the study treatment, the interventions required to treat it, and the outcome.

Progression of malignancy (including fatal outcomes), if documented by use of appropriate method (Cheson criteria), should not be reported as a serious adverse event.

Adverse events separate from the progression of malignancy (example, deep vein thrombosis at the time of progression or hemoptysis concurrent with finding of disease progression) will be reported as per usual guidelines used for such events with proper attribution regarding relatedness to the drug.

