### 11.3. Documentation and reporting of Pericardial Events

Since pericardial abnormalities (e.g., pericarditis, pericardial effusion and hemodynamic compromise) exist along a continuum with overlap between the clinical symptomatology and diagnoses, each pericardial AE (including grading of severity for each individual event) along the continuum should be captured separately (Table 11-1).

Table 11-1. Defin	Table 11-1. Definitions of Pericardial Events			
Event Term	Definition	Characteristics/Diagnosis		
Pericarditis	Inflammation of the pericardium	The major clinical manifestations of acute pericarditis include: 1) chest pain, 2) pericardial friction rub, 3) ECG changes (with new widespread ST elevation or PR depressions), and 4) pericardial effusion. At least 2 of these features are usually considered necessary to make the diagnosis.		
Pericardial effusion	Excess exudate, or fluid, in the pericardium	Once a pericardial effusion is suspected, the diagnostic approach consists of 3 steps: 1) establish the presence of effusion, 2) assess the hemodynamic impact, and 3) establish the cause. Clinical evaluation and ECG findings may suggest the presence of a pericardial effusion, but imaging, usually ECHO, is required to establish a diagnosis.		
Hemodynamic Compromise	Mechanical compression of the heart by large amounts of fluid or blood within the pericardial space that limits the normal range of motion and function of the heart	The diagnosis of hemodynamic compromise is based upon clinical and imaging evidence. The following physical findings 1) sinus tachycardia, 2) elevated jugular venous pressure, and 3) pulsus paradoxus are suggestive of frank tamponade. ECHO or other imaging of the pericardium is essential to the diagnosis of hemodynamic compromise.		

All pericardial findings, regardless of seriousness and relationship to study medication, should be reported to the IRB/PB and MethylGene/Mirati. When reporting pericardial events, available ECHO results/reports (or other means of diagnosis if available) should also be provided. All cardiac events, including pericardial findings will be reported to the DSMB to facilitate their ongoing evaluation of safety in subjects treated in this study. Serious pericardial AEs are to be reported according to the standard procedure for reporting of SAEs.

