Event free survival (defined as time from the date of treatment start to the date of the first documented progressive disease (PD) or death due to any cause) rate using mocetinostat in this selected population will be estimated by the Kaplan-Meier method. For subjects achieving objective response as assessed by investigators, their duration of response is defined as the time from the date of first occurrence of CR or PR whichever is recorded first to the date of the first objectively documented progressive disease (PD) or death due to any cause. The duration of response will be assessed based on the sub-cohort of patients who showed responses also using Kaplan-Meier. To assess the safety and tolerability of mocetinostat, all toxicities related to the treatment will be tabulated and summarized by type and severity for illustration. Adverse events requiring discontinuation of study drug will be summarized and tabulated separately.

Other exploratory objectives include correlation of myc and Bcl-2 positivity with treatment response, assessment of mechanisms of resistance to mocetinostat via information on additional gene sequencing by IMPACT and Foundation Medicine, and analysis of T cell activation and exhaustion in the peripheral blood. For the former, myc and Bcl-2 positivity will be determined by IHC as binary factors which will be correlated with treatment response by Fisher's exact test. The laboratory genetic mutation study will be mostly descriptive for future references. A panel of mutations included in Table 10-2 will be examined for their presence/absence before and after treatments. Analysis of T cell activation and exhaustion will be over 3 timepoints. Due to the expected small sub-sample size, we may only be able to summarize the T cell activation and exhaustion markers measurements. However, if there are >5 responders and >5 non-responders, then Wilcoxon rank sum tests will be used to preliminary assess the correlation between these markers and the response.

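### Section 14's safety tables omit adverse events, including pericardial ones, that are judged unrelated and do not stop study drug

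*Combined protocol and SAP*

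**What the plan says.** Section 2.2 makes safety and tolerability a secondary objective. Section 14 meets it with two outputs. In the first, "all toxicities related to the treatment will be tabulated and summarized by type and severity for illustration". In the second, "Adverse events requiring discontinuation of study drug will be summarized and tabulated separately", with no attribution condition. Section 10.3 also has laboratory data summarised by CTCAE grade. No all-cause AE table, serious AE table or pericardial table is planned.

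Collection is wider than analysis. Section 11.1.1 states: "Adverse events that begin or worsen after informed consent should be recorded in CRDB". Attribution is an attribute of each recorded event, not a condition for recording it.

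Pericardial events get special treatment in Section 11.3: "All pericardial findings, regardless of seriousness and relationship to study medication, should be reported to the IRB/PB and MethylGene/Mirati". The same section sends them to the monitoring board and asks for each pericardial AE to be captured and graded separately. Under Section 9.3.4, "ECHOs will categorize pericardial fluid as minimal (or trivial), small, moderate or large and will assess for hemodynamic compromise".

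**The concern.** Section 11.3 treats the investigator's attribution as the wrong filter for pericardial findings, yet Section 14 brings that filter back at the analysis. Three features of the trial make this matter.

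- The trial is single-arm and open-label. Attribution is an unblinded judgement, and there is no control rate to check it against. An all-cause count does not depend on that judgement.
- Section 3.2.8 reports that enrolment in the earlier DLBCL/FL study was interrupted while a possible link to pericardial events was investigated.
- The background rates in Tables 3-5 to 3-7 carry no attribution filter. A count restricted to related events could not be set beside them.

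What is at stake is the final safety summary. The filter applies to every AE; pericardial events are where it is most visible.

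**Working it through.** **Step 1: which events fall outside both tables.** Section 14 gives no safety figure to reproduce, so the check is of the text. An event is tabulated if it is judged related or if it requires discontinuation. It is missed if it is judged unrelated and drug continues.

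| Pericardial event | Effect on study drug | In a planned table if judged unrelated? |
|---|---|---|
| Moderate or large effusion, or hemodynamic compromise | Removal required (9.3.4) | Yes, discontinuation table |
| Small new effusion, recorded as an AE | Continues unless it progresses (9.3.4) | No, unless drug is stopped |
| Pericarditis without the above | No removal rule in 9.3.4 or 9.3.5 | No, unless drug is stopped |
| Minimal or trivial new effusion, if recorded as an AE | May continue (9.3.4) | No, unless drug is stopped |

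Section 9.3.5 notes that early pericarditis may show no effusion. Table 9-3 covers drug-related toxicity only. Its pericardial footnote cites Section 6.2.2, which does not exist; Section 9.3.4 is the evident target.

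**Step 2: scale.** Table 3-7 gives 80 earlier NHL patients, 8 with any pericardial finding and 3 with a serious one. Its percentages reproduce: 8/80 = 10.0% and 3/80 = 3.75%, printed as 3.8. Intervals below are exact (Clopper-Pearson) 95%.

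- Non-serious: 8 − 3 = 5; 5/80 = 6.3% (2.1 to 14.0%).
- At 56 patients: 0.0625 × 56 = 3.5 (1.2 to 7.8).
- At 20 patients, if both cohorts stop after stage 1: 0.0625 × 20 = 1.3 (0.4 to 2.8).
- Pericarditis, all cancers (Table 3-6, with the 435 patients of Table 3-7): 6/435 = 1.4% (0.5 to 3.0%); × 56 = 0.8 (0.3 to 1.7). All six cases were serious.

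**Step 3: from events to omissions.** The expected number omitted is 3.5 × s, where s is the share judged unrelated and kept on drug. The documents do not give s. Over its whole range from 0 to 1, the number runs from 0 to 3.5, or to 7.8 at the upper confidence limit. A serious event can also be missed if judged unrelated with drug continued, since no serious AE table is planned. Counting all findings, the ceiling is 0.10 × 56 = 5.6.

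**Step 4: echocardiogram entry.** For abnormal laboratory values or test results, Section 11.1.1 says that "test results occurring after informed consent constitute adverse events only if they induce clinical signs or symptoms, are considered clinically significant", or if they need therapy or a change in study medication. Section 10.4 says: "In case of clinically significant abnormalities, they should be reported in CRDB". That sentence follows one about for-cause evaluation and neither requires nor excludes entry of scheduled results. Section 11.3 does not name CRDB as the destination for pericardial findings. Section 16.1 does name CRDB as the data-collection system, with data going to the IRB and the manufacturer.

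**The case against.** The strongest reply is that the gap is narrow. Section 11.1.1 sets a low bar for relatedness, a reasonable possibility, and pericardial toxicity is a known concern with this drug, so few such events would be called unrelated. The pericarditis example is expected in fewer than one patient before either filter is applied. The 5/80 base mixes serious-event reports, database searches, CT review and limited echocardiographic monitoring. This trial schedules echocardiograms for everyone, which could raise detection, and excludes present or past effusion and pericarditis, which could lower incidence. Nothing in Section 14 bars an analyst from adding an all-cause listing. All of this stands and keeps the point small. It does not remove the omission, because Section 14 states which events are tabulated and does not commit to more.

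A reader might go further and infer that low-grade echocardiogram findings never reach the dataset. The documents do not support that. Table 11-1 lists pericardial effusion as an event term, Section 11.3 requires all pericardial findings to be reported, and Section 16.1 makes CRDB the natural route. Entry is implied but not stated, so this is a matter for clarification.

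A reader might also take the earlier prospective echocardiogram series, 13 of 35, as a loss estimate (13/35 × 56 = 20.8 patients). That would be wrong: all 13 were minimal, trivial or small, and Section 9.3.4 regards minimal or trivial fluid as physiological.

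**Conclusion.** The point holds as a limitation of the planned analysis. An AE judged unrelated that does not stop study drug is collected but is in no planned AE table, and pericardial AEs are not exempt. For non-serious pericardial events the pool at risk is about 3.5 of 56 patients (1.2 to 7.8), assuming the earlier NHL rate carries over. The number actually omitted is some unknown part of that, possibly none.

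It would be wrong to infer that patients are less protected or that important effusions vanish from the results. Moderate, large or hemodynamically significant effusions require removal and so are tabulated. Reporting to the IRB/PB, the manufacturer and the monitoring board is intact, and the primary endpoint and decision rule are untouched. This is an inexpensive improvement that the sponsor could make, not a defect that must be corrected.

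**What to change.** In Section 14, replace the related-only table with a table of all AEs by type and severity regardless of attribution, with treatment-related AEs as a subset. Present it per subtype, as Section 14 already requires for objectives other than the primary. Add:

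- a pericardial line: treated patients with any pericardial event and with a serious one;
- treated patients by worst new post-baseline effusion category, with minimal or trivial shown separately from small or larger, and a row for no post-baseline echocardiogram.

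The restriction to new effusions matters. Section 10.4 uses the echocardiogram to establish baseline effusion, and the Section 9.3.4 rules for small and minimal effusions cover those absent at baseline. Without it, baseline fluid could be counted as on-treatment.

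In Section 10.4, state that the Section 9.3.4 effusion category from each echocardiogram is entered in CRDB, whatever its clinical significance or attribution.

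The cost is one wider table and one data field per echocardiogram already performed and graded. Section 10.4 schedules 5 to 6 per patient, depending on whether the screening study serves for Day 1: 5 × 56 = 280 to 6 × 56 = 336 entries, plus any effusion follow-up or for-cause studies. No procedure or reader is added. The downside is a higher reported AE and pericardial rate, part of it normal fluid, which is why the minimal category is shown separately.

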### 15.1 RESEARCH PARTICIPANT REGISTRATION AND RANDOMIZATION PROCEDURES

### 15.2 Research Participant Registration

Confirm eligibility as defined in the section entitled Criteria for Patient/Subject Eligibility.

Obtain informed consent, by following procedures defined in section entitled Informed Consent Procedures.

During the registration process registering individuals will be required to complete a protocol specific Eligibility Checklist.

All participants must be registered through the Protocol Participant Registration (PPR) Office at Memorial Sloan-Kettering Cancer Center. PPR is available Monday through Friday from 8:30am – 5:30pm at [contact]. Registrations must be submitted via the PPR Electronic Registration System (http://ppr/). The completed signature page of the written consent/RA or verbal script/RA, a completed Eligibility Checklist and other relevant documents must be uploaded via the PPR Electronic Registration System.

### 15.3 Randomization

Randomization will not be necessary for this study. After meeting inclusion and exclusion criteria, patients are eligible for this single arm open label study.

### 16.1 DATA MANAGEMENT ISSUES

A Research Study Assistant (RSA) will be assigned to the study. The responsibilities of the RSA include project compliance, data collection, abstraction and entry, data reporting, regulatory monitoring, problem resolution and prioritization, and coordination of the activities of the study team.

The Clinical Research Database (CRDB) will be used for data collection. The data will be reported to the institution (IRB) and the drug manufacturer (MethylGene/Mirati) as appropriate.

Tumor slides will be stored in the pathology department. Results from laboratory studies will photomicrographs of immunohistochemical studies and computer files of sequencing data. These files will be stored on the Department of Medicine server. Documentation linking patient identifiers, patient samples, and results will be securely maintained in the CRDB with access limited to study investigators.

### 16.2 Quality Assurance

Routine registration reports will be generated to monitor patient accruals and completeness of registration data. Routine data quality reports will be generated to assess missing data and inconsistencies. Accrual rates, extent, and accuracy of evaluations and followup will be monitored periodically throughout the study period and potential problems will be brought to the attention of the study team for discussion and action.

Random sample data quality and protocol compliance audits will be conducted by the study team at a minimum of twice a year and more frequently if indicated.

### 16.3 Data and Safety Monitoring

The Data and Safety Monitoring (DSM) Plans at Memorial Sloan Kettering Cancer Center were approved by the National Cancer institute in September 2001. The plans address the new policies set forth by the NCI in the document entitled "Policy of the National Cancer Institute for Data and Safety Monitoring of Clinical Trials" which can be found at: http://www.cancer.gov/clinicaltrials/conducting/dsm-guidelines/page1

The MSKCC Data and Safety Monitoring Plans can be found on the MSKCC Intranet at:

http://mskweb2.mskcc.org/irb/index.htm

There are several different mechanisms by which clinical trials are monitored for data, safety and quality. There are institutional processes in place for quality assurance (e.g., protocol monitoring, compliance and data verification audits, therapeutic response, and staff education on clinical research QA) and departmental procedures for quality control, and there are two institutional committees that are responsible for monitoring the activities of our clinical trials programs. The committees: Data and Safety Monitoring Committee (DSMC) for Phase I and II clinical trials, and the Data and Safety Monitoring Board (DSMB) for Phase III clinical trials, report to the Center's Research Council and Institutional Review Board.

During the protocol development and review process, each protocol will be assessed for its level of risk and degree of monitoring required. Every type of protocol (e.g., NIH sponsored, in-house sponsored, industrial sponsored, NCI cooperative group, etc.) will be addressed and the monitoring procedures will be established at the time of protocol activation.

